### Participant and Disease Characteristics

2. Have a diagnosis of plaque psoriasis (with or without PsA) for at least 6 months before the first administration of study intervention.
3. All participants must meet the following disease severity criteria at screening and at baseline:
  - a) Overall IGA 3 (moderate) plaque psoriasis  
AND
  - b) BSA 2-15% with at least 1 plaque outside of special sites  
AND
  - c) Involvement of at least 1 special site with at least moderate severity. Qualifying sites include scalp with ss-IGA  $\geq 3$ , face with f-IGA  $\geq 3$ , intertriginous with i-IGA  $\geq 3$ , or genital with sPGA-G  $\geq 3$ .
4. Be inadequately controlled with or intolerant of at least 1 prior topical therapy (including, but not limited to, corticosteroids, retinoids, vitamin D, or vitamin D/steroid and retinoid/steroid combinations, tacrolimus, pimecrolimus, anthralin/dithranol, coal tar preparations, tapinarof, roflumilast, etc.) for the treatment of psoriasis at both screening and baseline.
5. Be a candidate for phototherapy or systemic treatment for psoriasis (either naïve or history of previous treatment; see Exclusion Criterion 6 for washout of prior treatments).
6. Be considered, in the opinion of the investigator, suitable candidates for guselkumab therapy according to their country's approved product labeling.

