4. POPULATIONS (ANALYSIS SETS) FOR ANALYSIS

The analysis sets and the descriptions are defined below in [Table 6](#).

Table 6: Analysis Sets

Analysis Sets	Description
Enrolled	All participants who signed the informed consent form (ICF). This analysis set will be used for summarizing the overall study completion/withdrawal information.

Table 6: Analysis Sets

Analysis Sets	Description
Full Analysis Set (FAS) -Efficacy Analysis Set	All participants who were randomized in the study. This analysis set will be used for the efficacy analyses.

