13. Proportion of participants who achieve an f-IGA score of clear (0) or minimal (1) with at least 2-grade improvement from baseline at Week 16 among randomized participants with an f-IGA score ≥ 2 at baseline.
14. The change from baseline in individual scale score of PSSD components at Week 16
15. The proportion of participants who achieve a PSSD individual scale score of 0 at Week 16 among randomized participants with scale score ≥ 1
16. The proportion of participants who achieve a PSSD symptom score = 0 at Week 16 among randomized participants with PSSD symptom score ≥ 1
17. The proportions of participants who achieve a PSSD symptom score = 0 and a PSSD sign score = 0 and the proportion of participants who achieve a PSSD individual scale score of 0 for participants with a baseline symptom score, sign score, and each PSSD individual baseline scale score that is ≥ 1 over time through Week 16
18. The proportion of participants with Dermatology Life Quality Index (DLQI) 0/1 at Week 16

19. The change from baseline in patient-reported outcomes measurement information system-29 (PROMIS-29) score over time through Week 16

5.4.2.2. Definition of other efficacy endpoint (s) through Week 16

Details refer to section [5.4.1.1.](#) and [5.4.2.5.](#)

5.4.2.3. Analysis method of other efficacy endpoint(s) through Week 16

Other efficacy endpoints through Week 16 will be tested regardless of the significance of the primary and major secondary endpoints; the testing of these endpoints will not be controlled for multiplicity. All statistical testing will be performed at the 2-sided 0.05 significance level. Nominal (unadjusted) p-values will be presented.

The analyses of these other efficacy endpoints through Week 16 will be based on FAS and special site analysis sets for the endpoints related to the special sites.

Descriptive statistics (i.e., N, mean, median, SD, IQ range, minimum, and maximum) will be used to summarize continuous variables. Counts and percentages will be used to summarize categorical variables. Graphical data displays (e.g., line plots) may also be used to summarize the data.

The comparisons of interest will be between guselkumab group and the placebo group.

The primary estimand approach and analysis methods specified for the primary endpoint in Sections [5.3.2.](#) and [5.3.3.](#), will apply to all continuous endpoints, binary endpoints, and time to event endpoints.

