 15. The proportion of participants achieving NAPSI 0 over time through Week 48 among randomized participants with nail psoriasis at baseline.
 16. The change from baseline in Psoriatic Arthritis Impact of Disease score (PsAID-12) over time through Week 48
 17. The proportion of participants with a score suggestive of PsA, i.e., ≥ 3 on the Psoriasis Epidemiology Screening Tool (PEST) over time through Week 48 among randomized participants with screening PEST score < 3
 18. The change from baseline in PSSD symptom score over time through Week 48
 19. The proportion of participants who achieve ≥ 4 -point reduction (improvement) in PSSD itch score from baseline over time through Week 48 among participants with a PSSD itch score ≥ 4 at baseline.
 20. The proportion of participants with PSSD Individual Symptom Scale Score = 0 over time through Week 48 among participants with PSSD > 0 at baseline
 21. The change from baseline in individual scale score of PSSD components over time through Week 48.
 22. The proportion of participants who achieve a PSSD individual scale score of 0 over time through Week 48 among randomized participants with scale score ≥ 1
 23. The proportion of participants who achieve a PSSD symptom score = 0 over time through Week 48 among randomized participants with PSSD symptom score ≥ 1

-
24. The proportions of participants who achieve a PSSD symptom score =0 and a PSSD sign score =0 and the proportion of participants who achieve a PSSD individual scale score of 0 for participants with a baseline symptom score, sign score, and each PSSD individual baseline scale score that is ≥ 1 over time through Week 48
 25. The proportion of participants with Dermatology Life Quality Index (DLQI) 0/1 over time through Week 48
 26. The proportion of participants with DLQI 0 over time through Week 48
 27. The change from baseline in PROMIS-29 score over time through Week 48
 28. Change from baseline in Body Surface Area (BSA) affected over time through Week 48
 29. Change from baseline in total Psoriasis Area Severity Index (PASI) score over time through Week 48

5.4.2.5. Definition of other efficacy endpoint (s) through Week 48

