5.4.2.5.1. Dermatology Life Quality Index (DLQI)

The DLQI is a dermatology-specific quality of life instrument designed to assess the impact of the disease on a participant's quality of life. It is a 10-item questionnaire that, in addition to evaluating overall quality of life, can be used to assess 6 different aspects that may affect quality of life: symptoms and feelings, daily activities, leisure, work or school performance, personal relationships, and treatment. The DLQI is calculated by summing the score of each question resulting in a maximum of 30 and a minimum of 0. A higher score indicates more severe disease.

A score of ≤ 1 indicates no effect at all of disease on participant's health related quality of life, and a reduction of 5 points or more in total DLQI score is considered clinically meaningful improvement.

For a partially answered questionnaire (eg, not all 10 answers in the DLQI questionnaire were available):

- If one question's answer is not available, this question will be scored 0. The total score will then be calculated.
- If two or more questions' answers are unavailable, the questionnaire is not scored. Hence, the total score and each of the 6 component scores will be set to missing.
- If one question from one of the 6 component scores is missing, the affected component score will be set to be missing.

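### The DLQI 0/1 and DLQI 0 endpoints carry no baseline DLQI condition, so a participant who starts and stays at target counts as a responder without having improved

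*SAP*

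**What the plan says.** **Endpoint.** SAP 5.4.2.1 item 18 (also SAP Table 2 item 37 and Protocol Section 3) reads "The proportion of participants with Dermatology Life Quality Index (DLQI) 0/1 at Week 16". It compares guselkumab with placebo. SAP 5.4.2.4 items 25 and 26 (Table 2 items 45 and 46) follow DLQI 0/1 and DLQI 0 to Week 48; the latter reads "The proportion of participants with DLQI 0 over time through Week 48". Table 2 assigns both to the guselkumab group only. None of the three has a baseline or change-from-baseline clause.

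**Denominator.** SAP 5.4.2.3 states: "The analyses of these other efficacy endpoints through Week 16 will be based on FAS and special site analysis sets". DLQI is not a special-site endpoint, so the FAS applies: "All participants who were randomized in the study. This analysis set will be used for the efficacy analyses". SAP 5.4.2.4 also names the FAS for the Week 48 list.

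**Eligibility.** Protocol 5.1, criterion 3: "All participants must meet the following disease severity criteria at screening and at baseline". These are overall IGA 3, "BSA 2-15% with at least 1 plaque outside of special sites", and at least one special site scored 3 or higher. No inclusion or exclusion criterion sets a DLQI minimum.

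**Meaning of the target.** SAP 5.4.2.5.1: "A score of ≤ 1 indicates no effect at all of disease on participant's health related quality of life". That section otherwise gives a meaningful-change threshold of 5 points, which the endpoints do not use, and rules for partly completed questionnaires.

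**The concern.** A threshold proportion is normally read as the share of patients brought to the threshold. That reading fails for anyone already there at Week 0. Such a participant counts as a response if DLQI is still 0 or 1 at the visit, the value is not missing, and no intercurrent event in category 1 or 2 has occurred.

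The SAP guards against this elsewhere. PSSD scores of 0 require a baseline above 0 or of at least 1, and the itch response requires a baseline of at least 4. The NPF acceptable-response proportion requires baseline BSA above 3%, and PEST of 3 or more requires a screening score below 3. IGA 0/1 and BSA of 1% or less are protected by the entry criteria. DLQI 0/1 and DLQI 0 have neither protection.

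The interpretation of the trial's dermatology-specific quality-of-life measure is at stake. The Week 16 difference may be diluted, and the guselkumab-only rates to Week 48 mix improvement with starting status and have no control rate beside them.

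**Working it through.** The plan states no DLQI rate, power or baseline distribution, so there is no figure to reproduce. What follows is algebra plus labelled assumptions.

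**1. General formula.** Let q be the share of the FAS at target at Week 0, equal in both arms in expectation. Let s be the chance that such a participant is still at target at Week 16, and p the response rate in the rest, with subscripts G and P for the arms.

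- Arm rate = q·s + (1−q)·p
- FAS difference = (1−q)·(pG − pP) + q·(sG − sP)

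If sG = sP, the second term vanishes and the difference shrinks by (1−q), whatever the common value of s.

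**2. Range for q (assumed).** True DLQI was simulated as gamma-distributed, with independent visit error, rounding and no treatment effect, in 400,000 participants per scenario. The visit-to-visit SD of the difference was 1.5 to 3.5 points.

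| Baseline mean / SD | Share at DLQI 0/1 at Week 0 |
|---|---|
| 6 / 5 | 15.5% to 19.7% |
| 8 / 6 | 8.3% to 12.5% |
| 10 / 6 | 2.5% to 5.7% |
| 12 / 6 | 0.6% to 2.3% |

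In the middle case (mean 8, SD of the difference 2.5), 10.3% are at 0/1 at Week 0 and 10.3% at Week 16, against 6.5% at Week 16 among those with baseline above 1. The implied retention is (0.103 − 0.897 × 0.065) / 0.103 ≈ 43%. Across all scenarios it runs from 21% to 60%.

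**3. Dilution with equal retention.** Take assumed rates of 50% and 10% among those with baseline above 1, a difference of 40 points.

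- q = 2.5%: 0.975 × 40 = 39 points
- q = 10%: 0.90 × 40 = 36 points
- q = 20%: 0.80 × 40 = 32 points

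**4. Unequal retention.** With q = 10%, sG = 90% and sP = 43% (illustration only): 36 + 0.10 × (90 − 43) = 36 + 4.7 = 40.7 points. The dilution is gone.

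**5. Effect on a single arm's rate.** The shift against the restricted rate is q·(s − p). For placebo with q = 10% and p = 10%: at s = 43% the rate is 0.10 × 43 + 0.90 × 10 = 13.3%; at s = 90% it is 9 + 9 = 18%. For guselkumab with p = 50%: at s = 43% the shift is 0.10 × (43 − 50) = −0.7 points; at s = 90% it is +4 points. The sign for guselkumab is not fixed.

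**6. Power of the nominal Week 16 test.** Assume 40% versus 10% among those with baseline above 1, and s = 1 in both arms. At q = 10% the FAS rates are 46% and 19%, with power 0.998; the restricted set (about 180 versus 90) has 0.9999. At q = 20% the values are 0.983 and 0.9997. Restriction costs no power in this setting.

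**The case against.** The endpoint as written is a legitimate quantity: the proportion of all randomized participants whose quality of life is unaffected at the visit. It keeps the randomized denominator, and randomization balances baseline status in expectation. It sits outside the fixed testing sequence with nominal p-values, and results after Week 16 are only summarized by visit. All of this stands and limits the weight of the point.

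It is tempting to say that participants at 0/1 cannot benefit. The documents do not support that. Topicals are stopped at least 2 weeks and systemics or phototherapy at least 4 weeks before the first dose, and such treatments are prohibited during the study. A placebo participant at 0/1 can therefore worsen, and staying there can itself be a treatment effect.

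A reader might also infer that low baseline DLQI is common because BSA is low. The protocol argues the reverse: its rationale stresses the heavy impact of low-BSA special-site disease, and entry requires at least moderate special-site severity and inadequate control with, or intolerance of, a topical. The share may be very small.

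Nothing else in the SAP settles the matter. The baseline DLQI subgroup splits at 10 and serves the primary and selected major secondary endpoints. The non-exhaustive list of baseline characteristics in Appendix 2 does not name DLQI. By-visit summaries may show the Week 0 count, but the SAP does not say so.

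**Conclusion.** The point holds as a modest, inexpensive improvement. On the text it is certain that these endpoints have no baseline condition and that eligibility does not supply one. The size is uncertain: q is not in the documents, and 0.6% to 20% rests on the assumed distributions above. The loss of q × 40 points (4 at q = 10%) rests further on assumed response rates and on equal retention in the two arms; with more worsening on placebo it is smaller or nil.

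Three stronger readings should not be drawn. First, the placebo rate is not shown to nearly double: that needs about 90% retention, whereas the no-effect simulation implies about 43% in the middle case, giving 13.3% rather than 18%. Second, there is no type I error problem and no expected bias toward guselkumab. Third, the guselkumab rates to Week 48 are not necessarily inflated, since the shift can take either sign. What the change buys is a response rate that can be read as improvement.

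**What to change.** - In SAP Table 2 items 37 and 45, 5.4.2.1 item 18 and 5.4.2.4 item 25 (DLQI 0/1), add: *among randomized participants with baseline DLQI >1*.
- In Table 2 item 46 and 5.4.2.4 item 26 (DLQI 0), add the same clause with *baseline DLQI >0*.
- Protocol Section 3 has the unrestricted wording. Either record the departure in the SAP, or keep the FAS version alongside as a supplementary analysis.
- Report by arm the number at DLQI 0/1 at Week 0.
- State how a missing baseline DLQI is handled, because the restricted denominator now depends on it.
- Keep non-responder imputation and the existing intercurrent-event rules.

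The cost is SAP wording and one filter on a variable already collected at Week 0. The denominator falls by the share q, for example from 300 to about 270 at q = 10%. The restricted rate no longer describes all randomized participants, which is the reason to keep the FAS version available.

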reported outcomes	
group
 
 1. Change from baseline in BSA x IGA through Week 16 
The following endpoints relate to guselkumab group only
 
 2. Change from baseline in BSA x IGA over time through Week 48 3. The proportion of participants who achieve NPF target response (i.e., BSA\leq1%) over time through Week 48 4. The proportion of participants who achieve NPF acceptable response (i.e., BSA \leq3% or BSA75) over time through Week 48 among those with baseline BSA >3% 5. The proportion of participants who achieve PASI 50/75/90/100 over time through Week 48 6. The proportion of participants who achieve IGA 0 over time through Week 48 7. The proportion of participants who achieve IGA 0/1 over time through Week 48 8. Time to achievement of NPF target response (i.e., BSA \leq1%) through Week 48 9. Time to achievement of NPF acceptable response (i.e., BSA\leq3% or BSA75) through Week 48 10. The proportion of IGA 0/1 Week 16 responders who maintain IGA 0/1 response at Week 48 11. Change in BSA over time through Week 48 12. Change in PASI over time through Week 48 
Other Endpoints – Special Site Efficacy
 
The following endpoints will compare the guselkumab with the placebo group
 
Scalp
 
 13. Time to complete scalp psoriasis clearance (ss-IGA = 0) through Week 48, among randomized participants with scalp psoriasis at baseline 14. Proportion of participants with complete scalp psoriasis clearance (ss-IGA = 0) over time among randomized participants with scalp psoriasis at baseline over time through Week 16 15. Proportion of participants who achieve an ss-IGA score of absence of disease (0) or very mild disease (1) with at least 2-grade improvement from baseline at Week 16 among randomized participants with an ss-IGA score \geq2 at baseline 
Genital
 
 16. Time to complete genital psoriasis clearance (sPGA-G = 0) through Week 48, among randomized participants with genital psoriasis at baseline 17. Proportion of participants with complete genital psoriasis clearance (sPGA-G = 0) among randomized participants with genital psoriasis at baseline over time through Week 16 18. Proportion of participants who achieve an sPGA-G score clear (0) or minimal (1) with at least 2-grade improvement from baseline at Week 16 among randomized participants with an sPGA-G score \geq2 at baseline

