5.3.2. Estimand**5.3.2.1. Primary Estimand (Estimand 1)**

The primary endpoint is the proportion of participants achieving an IGA score of 0/1 response at Week 16. This endpoint will be analyzed based on the estimands defined by the following 5 components:

- **Population:** Participants with low body surface area (BSA) moderate plaque psoriasis with special site involvement.
- **Treatment:**
 - Placebo
 - Guselkumab
- **Variable (Endpoints):** The proportion of participants who achieve an Investigator's Global Assessment (IGA) score of cleared (0) or minimal (1) at Week 16. Participants who have intercurrent events (ICEs) 1-2 (defined below) prior to Week 16 will be considered as not achieved for IGA 0/1 response, regardless of the observed data.
- **Intercurrent Events (ICEs):** The following are the ICEs and corresponding strategies for this trial.
 1. Initiated protocol prohibited medications/therapies for psoriasis, except for the following
 - a) If the prohibited medication is a corticosteroid and was used for an indication other than psoriasis and for ≤ 2 weeks (short term use)
 - b) If the prohibited medication is a corticosteroid and the mode of delivery is inhaled, otic, ocular, nasal or other route of mucosal delivery.
 2. Discontinued study intervention due to lack of efficacy (e.g., lack of efficacy or an AE of worsening of psoriasis)
 3. Treatment discontinuation due to reasons other than ICE 2.

ICE categories 1 to 2 will follow the composite strategy, where participants who meet them prior to Week 16 will be considered as nonresponders for IGA cleared (0) or minimal (1) response for the primary analysis, regardless of the observed data. The ICE category 3 will follow the treatment policy strategy, where participants who meet them prior to week 16, will use the observed values. For participants experiencing multiple ICEs, an ICE in categories 1 to 2 will supersede an ICE in category 3.
- **Population level summary:** Difference in proportion of participants who achieve an IGA score of cleared or minimal (IGA 0/1) between guselkumab and placebo at Week 16.

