5.4.2. Supportive Secondary Endpoint(s)

In addition to the primary and major secondary endpoints, other efficacy endpoints will also be analyzed.

This section outlines the definition and analyses of the other efficacy endpoints.

Other efficacy endpoints through Week 16 will be analyzed at Week 16 DBL and other efficacy endpoints through Week 48 will be analyzed at Final DBL.

5.4.2.1. Other efficacy endpoint through Week 16

1. Change from baseline in BSA \times IGA through Week 16.
2. Time to complete scalp psoriasis clearance (ss-IGA = 0) through week 16, among randomized participants with scalp psoriasis at baseline
3. Proportion of participants with complete scalp psoriasis clearance (ss-IGA = 0) over time among randomized participants with scalp psoriasis at baseline over time through Week 16.

4. Proportion of participants who achieve an ss-IGA score of absence of disease (0) or very mild disease (1) with at least 2-grade improvement from baseline at Week 16 among randomized participants with an ss-IGA score ≥ 2 at baseline.
5. Time to complete genital psoriasis clearance (sPGA-G = 0) through week 16, among randomized participants with genital psoriasis at baseline
6. Proportion of participants with complete genital psoriasis clearance (sPGA-G = 0) among randomized participants with genital psoriasis at baseline over time through Week 16.
7. Proportion of participants who achieve an sPGA-G score of clear (0) or minimal (1) with at least 2-grade improvement from baseline at Week 16 among randomized participants with an sPGA-G score ≥ 2 at baseline.
8. Time to complete intertriginous psoriasis clearance (i-IGA = 0) through week 16, among randomized participants with intertriginous psoriasis at baseline
9. Proportion of participants with complete intertriginous psoriasis clearance (i-IGA = 0) among randomized participants with intertriginous psoriasis at baseline over time through Week 16
10. Proportion of participants who achieve an i-IGA score of clear (0) or minimal (1) with at least 2-grade improvement from baseline at Week 16 among randomized participants with an i-IGA score ≥ 2 at baseline.
11. Time to complete facial psoriasis clearance (f-IGA = 0), through week 16, among randomized participants with facial psoriasis at baseline.
12. Proportion of participants with complete facial psoriasis clearance (f-IGA = 0) among randomized participants with facial psoriasis at baseline over time through Week 16.

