For continuous endpoints the MMRM model will be used to test the difference between guselkumab group and the placebo group. This model relies on the Missing at Random (MAR) assumption for the missing responses. Under the assumption of MAR, the missing data will be accounted for through correlation of repeated measures in the model.

The explanatory variables of the MMRM model will include treatment group, visit, baseline score, special site (scalp, face, intertriginous, genital), interaction term of visit with treatment group, and an interaction term of visit with baseline score. For endpoints related to special sites, the MMRM will not include special site as an explanatory variable.

The estimates of the treatment difference between guselkumab group and the placebo group will be provided by the difference in the least squares means (LS means). The 95% confidence interval (CI) for the differences in LS means and p-values will be calculated based on the MMRM. An unstructured covariance matrix for repeated measure within a participant will be used. The F-test will use Kenward-Roger's approximation for degrees of freedom.

Participants with an intercurrent event in category 1 or 2 prior to Week 16 will be considered to have zero change from baseline for that endpoint at Week 16. If a participant had any of the ICE category 3 prior to Week 16, observed value will be used from the visit.

For binary endpoints chi-square test or Cochran-Mantel-Haenszel chi-square test (as appropriate) will be used to compare the proportion of participants achieving selected endpoints between the guselkumab treatment group and the placebo group. The analyses will be stratified by special site (scalp, face, intertriginous, genital). In case of rare events, Fisher's exact test will be used for treatment comparisons.

Participants with an intercurrent event in category 1 or 2 prior to Week 16 will be considered non-responder for the binary endpoint at Week 16. If a participant had any of the ICE category 3, observed value will be used from the visit.

For time to event endpoints, life table estimates will be provided for the response rate (95% CI) and the time to achieve the endpoint by Week 16. P-value will be calculated based on log-rank test.

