For participants experiencing ICE's 1 or 2 will be censored. Observed value will be used for the response after the occurrence of ICE 3. For participants experiencing multiple ICEs, an ICE in categories 1 or 2 will supersede an ICE in category 3. Participants who do not achieve the endpoint by Week 16 will be censored for the analysis.

5.4.2.4. Other efficacy endpoints through Week 48

The other efficacy endpoints through Week 48 are listed below. The analyses will be based on full analysis set (FAS). Endpoints after Week 16 through Week 48 will be descriptively summarized by visit. The same missing data handling rules used in Week 16 DBL main analysis will be applied for all endpoints in the final DBL.

1. Change from baseline in BSA \times IGA over time through Week 48
2. The proportion of participants who achieve National Psoriasis Foundation (NPF) target response (i.e., BSA $\leq 1\%$) over time through Week 48
3. The proportion of participants who achieve NPF acceptable response (i.e., BSA $\leq 3\%$) over time through Week 48 among those with baseline BSA $> 3\%$
4. The proportion of participants who achieve PASI 50/75/90/100 over time through Week 48
5. The proportion of participants who achieve IGA 0 over time through Week 48
6. The proportion of participants who achieve IGA 0/1 over time through Week 48
7. Time to achievement of NPF target response (i.e., BSA $\leq 1\%$)
8. Time to achievement of NPF acceptable response (i.e. BSA $\leq 3\%$)

-
9. The proportion of patients who achieve IGA 0/1 at Week 16 and who maintain IGA 0/1 response at Week 48
 10. The proportion of participants achieving palmoplantar IGA (pp-IGA) of clear (0) or almost clear/minimal (1) with at least 2-point improvement over time through Week 48 among randomized participants with a pp-IGA score ≥ 2 at baseline
 11. The proportion of participants achieving pp-IGA of clear (0) over time through Week 48 among randomized participants with palmoplantar psoriasis at baseline
 12. The change from baseline in the Nail Psoriasis Severity Index (NAPSI) over time through Week 48 among randomized participants with nail psoriasis at baseline
 13. The percent improvement from baseline in NAPSI over time through Week 48 among randomized participants with nail psoriasis at baseline
 14. The proportion of participants achieving NAPSI 50/75/90/100 response over time through Week 48 among randomized participants with nail psoriasis at baseline

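### SAP 5.4.2.3 censors participants with ICE 1 or 2 in the time-to-clearance analyses, without a censoring time and against its own composite strategy, and SAP Table 2 gives these endpoints a different horizon

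*SAP*

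**What the plan says.** **Strategy.** SAP 5.4.2.3 states that the primary estimand approach and methods "will apply to all continuous endpoints, binary endpoints, and time to event endpoints". SAP 5.3.2.1 defines that approach: "ICE categories 1 to 2 will follow the composite strategy, where participants who meet them prior to Week 16 will be considered as nonresponders", whatever was observed. For binary endpoints, 5.4.2.3 follows it: "Participants with an intercurrent event in category 1 or 2 prior to Week 16 will be considered non-responder for the binary endpoint at Week 16". For continuous endpoints it sets zero change.

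**Time to event.** The same section plans that "life table estimates will be provided for the response rate (95% CI) and the time to achieve the endpoint by Week 16", with a log-rank p-value. Its ICE rule is that participants with ICEs "1 or 2 will be censored. Observed value will be used for the response after the occurrence of ICE 3". A later, separate sentence adds: "Participants who do not achieve the endpoint by Week 16 will be censored for the analysis". No date of censoring is given for ICE 1 or 2.

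**Horizon.** SAP Table 2, under a heading that compares guselkumab with placebo, lists as item 13 "Time to complete scalp psoriasis clearance (ss-IGA = 0) through Week 48, among randomized participants with scalp psoriasis at baseline". Items 16, 19 and 22 give the same horizon for genital, intertriginous and facial clearance. SAP 5.4.2.1 lists the scalp endpoint as "Time to complete scalp psoriasis clearance (ss-IGA = 0) through week 16, among randomized participants with scalp psoriasis at baseline", and the other three sites likewise. Protocol Section 3 states no horizon. Placebo participants cross over to guselkumab at Week 16 (SAP 1.2).

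**The concern.** Under a composite strategy, a participant who starts prohibited psoriasis therapy or stops for lack of efficacy has a known unfavourable outcome. Censoring that participant at the event treats the later outcome as unknown and assumes that clearance would have come as often as in those still at risk. ICE 2 is defined by lack of efficacy or worsening psoriasis, so that assumption is implausible and the censoring is informative. The life table would then describe clearance as if the ICE had not happened, which is not the estimand that 5.4.2.3 names. One report would treat the same ICEs as failure in the binary site endpoints and as missing information in the time-to-event endpoints.

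The horizon matters for a different reason. After Week 16 both arms are scheduled for guselkumab, so a comparison to Week 48 would set immediate against delayed treatment. SAP 5.4.2 also assigns Week 16 endpoints to the first database lock and Week 48 endpoints to the final one, so the horizon decides when these endpoints are analysed.

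**Working it through.** **The plan's own figure.** Neither document gives a clearance rate, an ICE rate or a power for time to clearance. The nearest figure is 90% power for the Week 16 site responses with 25 placebo and 50 guselkumab participants (SAP Table 4). With power = Φ[(Δ − 1.96·SE₀)/SE₁], SE₀ pooled and SE₁ unpooled, scalp (15% vs 52%) gives SE₀ = √(0.3967 × 0.6033 × (1/25 + 1/50)) = 0.1198 and SE₁ = √(0.15 × 0.85/25 + 0.52 × 0.48/50) = 0.1005. Power is Φ[(0.37 − 0.2349)/0.1005] = 91.1%. The same formula gives 91.0% for genital and intertriginous and 89.8% for face. Table 4 reproduces and is not in dispute.

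**Censoring: assumptions.** Visits are at Weeks 4, 8, 12 and 16. A composite clearance q by Week 16 is spread evenly over the four visits. A fraction f has ICE 1 or 2, spread evenly just after Weeks 4, 8 and 12, and does not clear. There is no other loss.

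**Formula.** Clearance = 1 − Π(1 − d_j/R_j), where d_j = q/4 and R_j is the fraction still at risk.

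- *ICE kept at risk to Week 16, q = 40%:* S = 0.9 × (0.8/0.9) × (0.7/0.8) × (0.6/0.7) = 0.60. Clearance is 40.0%, the composite rate.
- *ICE censored at occurrence, q = 40%, f = 10%:* R = 1, 0.8667, 0.7333, 0.6000. S = 0.9000 × 0.8846 × 0.8636 × 0.8333 = 0.573. Clearance is 42.7%.

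| ICE rate | Censored at ICE, composite 40% | Excess (points) | Censored at ICE, composite 5% | Excess (points) |
|---|---|---|---|---|
| 2% | 40.5% | 0.5 | 5.05% | 0.05 |
| 5% | 41.3% | 1.3 | 5.13% | 0.13 |
| 10% | 42.7% | 2.7 | 5.28% | 0.28 |
| 20% | 46.1% | 6.1 | 5.61% | 0.61 |
| 30% | 50.8% | 10.8 | 6.02% | 1.02 |

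An actuarial table that counts ICE participants as at risk for half an interval softens this without changing its direction. At f = 10%, S = 0.9 × (1 − 0.1/0.8833) × (1 − 0.1/0.75) × (1 − 0.1/0.6167) = 0.580, so clearance is 42.0%.

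**Arm difference.** The composite difference is 40 − 5 = 35.0 points.

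- 10% ICE in both arms: 42.70 − 5.28 = 37.4.
- 20% placebo, 5% guselkumab: 41.28 − 5.61 = 35.7.
- 20% placebo, 0% guselkumab: 40.00 − 5.61 = 34.4.

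The difference can rise or fall.

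**Horizon.** An unstratified log-rank test (SAP 5.1 drops stratification for site endpoints) was simulated 2,000 times with 25 vs 50 participants. The clearance hazard per four-week visit was constant, and placebo took the guselkumab hazard after Week 16. For assumed Week 16 clearance of 5% vs 40%, power was about 95% at Week 16 and 47% at Week 48. Over the four pairs tried (5% vs 30%, 5% vs 40%, 10% vs 40%, 10% vs 45%), the ranges were 76–95% and 28–47%. A Week 48 horizon would dilute the contrast.

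**The case against.** **The SAP does not say when censoring happens.** Censoring at Week 16 would satisfy both the ICE sentence and the composite strategy, and would raise nothing. This stands as a qualifier: censoring at the ICE is an inference. It is still the natural one, because the separate sentence already censors everyone not cleared by Week 16, so the ICE sentence would otherwise add little. On either reading the programmer lacks a date.

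**A reader might infer that life-table clearance will exceed the non-responder-imputed Week 16 proportion for the same site.** The documents do not support that. Time to clearance counts the first clearance at any visit; the binary endpoint counts clearance at a given visit. Someone who clears at Week 8 and relapses, or clears and then misses Week 16, is an event in one and a non-responder in the other. The two can differ with no censoring problem, and the repair would not make them equal.

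**A reader might infer that the treatment effect is inflated.** This is not established. Lack-of-efficacy discontinuation may well be commoner on placebo, and the arm difference has no fixed direction.

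**A reader might infer that a Week 48 test against placebo is planned.** The operative text does not plan one. SAP 1.2 places the comparison at Week 16, 5.4.2.3 estimates by Week 16, and 5.4.2.4 makes later summaries descriptive and omits these four endpoints. What remains is a conflict with Table 2, which the protocol cannot settle.

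**Conclusion.** The time-to-event ICE rule, on its natural reading, contradicts the estimand that the same section adopts, and on any reading it lacks a censoring time. If censoring is at the ICE, each arm's clearance estimate exceeds the composite rate whenever an ICE 1 or 2 precedes clearance. The excess is small when ICEs are rare (0.5 to 1.3 points at 2–5%, for 40% composite clearance) and reaches 6.1 points at 20%. In an arm with 5% clearance it is at most about 1 point, even at 30%. These sizes rest on assumed clearance and ICE rates and an assumed even spread over visits; the direction within an arm needs only that ICE participants count as not cleared and that others clear later.

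The Week 48 wording in Table 2 is an internal inconsistency to reconcile. Both matters concern other endpoints with nominal p-values outside the multiplicity scheme. The primary and the 12 major secondary endpoints have their own explicit ICE rules and are untouched.

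**What to change.** 1. In SAP 5.4.2.3, replace the ICE sentence for time-to-event endpoints: participants with ICE 1 or 2 before clearance stay in the risk set as not cleared and are censored at Week 16. State that a clearance observed after such an ICE is not an event, which is what the composite strategy implies.
2. In SAP Table 2, change items 13, 16, 19 and 22 to Week 16 for the comparison with placebo. If Week 48 curves are wanted, add them to 5.4.2.4 as descriptive displays by arm, without a test.

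The cost is a few lines of SAP text and one line in the time-to-event derivation, to be settled before the Week 16 lock. No new data are needed, and neither trial conduct nor sample size changes.
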